3.0 Innovation of Intervention to be Studied

Early mobilization is a widely accepted pillar of acute hospital physical therapy services. In most populations, early mobility is regarded as safe, feasible, and yields positive results.⁶ A considerable amount of clinical and scientific literature has evaluated and upheld the positive effect of early mobility on patient safety, ICU delirium, duration of mechanical ventilation, hospital length of stay, functional mobility, ambulation ability, and mortality. However, most of the research in the field of early mobilization has focused on intensive care patients with multiple medical comorbidities.⁷

The consideration of an acute stroke diagnosis in relation to the approach of acute care PT and "early mobility" is limited. The AVERT trial was novel in opening the doors to evaluate physical therapy's approach to acute stroke care on dedicated stroke units. This research proved critical since earlier research surmised that complications of immobility could be estimated to account for as many as 51% of death in the first 30 days post stroke.⁸ The results of the AVERT trial raised concern that very early mobilization may cause changes in cerebral blood flow and blood pressure leading to worsened stroke outcomes, increased mortality and increased rate of falls during early mobility.⁹

From the publication of the AVERT trial, there has been a rise in clinical interest regarding the correlation of early mobility and improved functional outcomes post stroke with the biggest question remaining- how early is too early and how much is too much? The majority of physical therapy studies in the acute stroke population have only examined the optimal time to begin mobilization post admission to the hospital.⁹ We hypothesize that the approach of shorter, more frequent sessions of intense quality therapy services will negate the post stroke cerebral perfusion factor. Thus, allowing patients to progress functional mobility with improved tolerance to therapy sessions, frequent repetition, as well as implementation of motor learning principles to ensure carryover by providing distributed over massed practice.

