If a patient is randomized to the frequent AND intense physical therapy treatment group they will receive PT services 2x/day for 3 out of the first 5 days of hospital admission and daily for the remainder of the hospitalization. Sessions will be 20-50 minutes in duration (based on patient tolerance) and will focus on increasing the intensity of services by making difficult tasks more difficult with the addition of resistance or other challenges. This is known as “Error Augmentation training” and will be implemented to target at least 3 post stroke deficits identified on evaluation. If a patient is randomized to the standard of care group they will receive the normal amount of PT services one a day, three to five days week for 20-50minutes throughout admission. The patient will be assisted to perform transfers and mobility tasks with a PT providing facilitation to assist the patient without the component of an added challenge.

Functional measures such as PASS, AMPAC, mRS will be collected on initial PT evaluation, day three of treatment and discharge from the acute care hospital. These measures will be collected again in the outpatient neurology clinic (or virtually via Zoom or Doxy.me) at 30 day follow up appointment. Study procedures will end after 30 day follow up appointment is completed.

Participants can ask to end PT sessions early if they become uncomfortable or do not want to do them.

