12.0 Outcomes and Analysis

Goal enrollment is 168 participants. Based on the past literature, in similar populations the standard deviation of PASS measurements is at the most 7.20.⁵ Using this, with a sample of 42 patients in each group, with 95% confidence at the end of the study we can estimate this difference within a margin of error of 2.8.

The primary outcome measure will be the change in postural assessment stroke scale scores from time of PT evaluation to hospital discharge. A factorial design will allow for a test of intensity (vs control) and duration (vs control) through pooling across treatment arms. Using the table below, margins (A+C, B+D, A+B, C+D) need to each be 104 given a mean difference of 2.8, standard deviation of 7.2, 80% power and 5% type I error. Given that this is an early phase study, we can increase the type I error to 10% which would decrease the overall sample size needed to 168 patients (42 per arm) whilst still maintaining 80% power.

	Low Intensity	High Intensity	Totals
Low Duration	A	B	A+B
High Duration	C	D	C+D
Totals	A+C	B+D	A+B+C+D

We are planning to conduct the analysis using intention to treat paradigm. In a preliminary analysis we will compute all summary statistics. Initial plots, such as spaghetti plots, will be used to guide our analyses. A general linear mixed model approach will be used to analyze all the outcomes. This model will account for the correlations between time points using either a compound symmetric or spatial structure for the covariance matrix. Post-hoc analyses using Tukey type adjustments will be performed to obtain least squares estimates of the differences between the two randomized groups. Although the study is powered based on only the primary

outcome (PASS), we will apply multiple comparisons adjustments for the rest of the outcomes, using Bonferroni corrections. We will test for the assumptions using diagnostic procedures and take appropriate actions if needed. Also, we will define an outcome to be ‘favorable’ or ‘unfavorable’ based on a threshold and apply generalized linear mixed models with logistic link and repeat the analyses. We will attempt to minimize drop-outs but in case of missing data, we will assume Missing at Random or Missing Completely at Random. If necessary, we will perform multiple imputations. For all analyses, we will use SAS, (MIXED, GLIMMIX, MI and MIANALYZE).

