15.0 Potential Benefits

The potential benefit to patient's is that the treatment they receive may prove to be more effective than the other study treatment or than other available treatments, although this cannot be guaranteed. Certain treatment arms may increase a patient's independence and may lead to a shorter hospital length of stay and improved functional mobility outcomes (i.e.: regaining the ability to stand and walk).

It is hoped that the information gained from the study will help in the treatment of future patients with similar conditions and that it will help the researcher learn more about physical therapy approach to mobility post stroke.

15.0 Sharing of results with subjects:

Results of the study will not be shared with the individual subjects

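### Section 12 relies on MAR or MCAR alone for every missing score and has no rule for death or for withdrawal because of deterioration

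*Combined protocol and SAP*

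**What the plan says.** Section 12.0 (Outcomes and Analysis) defines the primary endpoint: "The primary outcome measure will be the change in postural assessment stroke scale scores from time of PT evaluation to hospital discharge". On analysis it says "We are planning to conduct the analysis using intention to treat paradigm" and "A general linear mixed model approach will be used to analyze all the outcomes". Its whole provision for absent data is "We will attempt to minimize drop-outs but in case of missing data, we will assume Missing at Random or Missing Completely at Random", followed by "If necessary, we will perform multiple imputations". No missing-not-at-random analysis is named. The section also plans a favourable/unfavourable analysis against a threshold, without saying on which side a death falls.

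Section 9.0 has PASS, AMPAC and mRS scored at evaluation, day three and discharge. For 30 days it adds: "These measures will be collected again in the outpatient neurology clinic", or by video call. Each score needs a living patient who is assessed.

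Section 3.0 reports the concern raised by an earlier very-early-mobilisation trial, including "worsened stroke outcomes, increased mortality and increased rate of falls during early mobility". Section 13.0 gives death as an example of an adverse event. Mortality is not among the endpoints in Section 5.0. Vital status is not in the data list in Section 10.0, although complications are.

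Section 14.0 lets the investigators withdraw a patient for worsening, for instability that limits mobilisation, or for transfer to intensive care. It does not say whether outcomes are collected afterwards.

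**The concern.** Two groups will lack a discharge or 30-day score for reasons tied to how they fared: those who die, and those withdrawn because they got worse. A likelihood-based mixed model or multiple imputation under MAR predicts what a patient with the same earlier scores would have shown if still under observation. For a patient who has died, that quantity does not exist. For a patient withdrawn for deterioration, it is probably too favourable, because the event that caused the withdrawal is not fully captured by the evaluation and day-three scores. A patient lost before day three contributes only the evaluation score.

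If more active therapy caused more of these events, the active arm's functional means would rest on those who did well plus optimistic predictions for the rest. The bias would favour the arm doing harm, in a trial whose background section names that harm. Withdrawal for worsening is plausibly the more frequent of the two routes.

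**Working it through.** **1. The plan's own sample size.** Section 12.0 gives a difference of 2.8, SD 7.2 and 80% power. I assume a two-sided test. Per margin, n = 2(z₁₋α/₂ + z₀.₈)² × 7.2² / 2.8².
- α = 5%: 2 × (1.960 + 0.842)² × 51.84 / 7.84 = 104, as stated.
- α = 10%: 2 × (1.645 + 0.842)² × 51.84 / 7.84 = 82. The plan uses 84 (168 in total, 42 per arm), which gives 80.9% power.

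The sample size is sound on its inputs. It fixes the yardstick: a 2.8-point difference between margins of 84.

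**2. Shift per death in the primary outcome.** The documents give no death rate and no mean evaluation PASS. Assumptions: evaluation PASS B = 15 to 25, gain expected under MAR g = 4, death scored at the floor, taken as 0. MAR credits the patient with +g; the floor rule gives −B. The margin's mean change moves by −(B + g)/84 per death.
- B = 15: −19/84 = −0.23
- B = 25: −29/84 = −0.35
- Three excess deaths: −57/84 = −0.68 to −87/84 = −1.04
- As a share of 2.8: 0.68/2.8 = 24%; 1.04/2.8 = 37%

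**3. The same check as death rates.** Let survivors gain 1.82 (the Phase I standard-care change, Section 3.0) and 1.82 + 2.8 = 4.62. With death at 0, the difference is [(1 − p_T) × 4.62 − p_T × B] − [(1 − p_C) × 1.82 − p_C × B].

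| Deaths, treated vs control | B = 15 | B = 20 | B = 25 |
|---|---|---|---|
| 2% vs 2% | 2.74 | 2.74 | 2.74 |
| 5% vs 2% | 2.16 | 2.01 | 1.86 |
| 8% vs 2% | 1.57 | 1.27 | 0.97 |

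An analysis that models the dead as survivors stays near 2.8 in every row. With no control deaths, the benefit is cancelled at p = 2.8/(4.62 + B), which is 14.3% for B = 15 and 9.5% for B = 25, or about 12 and 8 deaths among 84.

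**4. Withdrawals for worsening.** If m patients in a margin are withdrawn and their true change is on average δ points below the MAR prediction, the margin's mean is overstated by m × δ/84. The documents give neither m nor δ, so I put no number on it.

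**5. Length of stay.** A stay that ends in death is observed, so the missing-data sentence does not govern it. If such stays are simply averaged in, the difference moves by −(p_T − p_C)(L − d). With mean stay L = 6 to 8 days and death at day d = 3 (assumed):
- 5% vs 2%: −0.03 × 3 to −0.03 × 5 = −0.09 to −0.15 day
- 10% vs 2%: −0.08 × 3 to −0.08 × 5 = −0.24 to −0.40 day

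Phase I reported a 1.5-day reduction (Section 3.0).

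**The case against.** **Deaths may be few or none.** Section 7.0 requires NIHSS 2-18, age 18-80, medical stability, full orientation and capacity to consent. It excludes haemorrhagic stroke, the group to which Sections 3.0 and 13.0 attribute the earlier trial's harm. The Phase I summary reports one significant adverse event and mentions no death. Only in-hospital deaths touch the primary outcome. This stands, and it is why the size is shown as a range that starts at zero.

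**MAR is not naive.** It conditions on evaluation and day-three scores, so a patient already declining is not given an average recovery. Scoring death at 0 is also a choice of estimand and not the true value. Both points stand. They are reasons to make the floor-score analysis a companion to the primary analysis and not its replacement.

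Some stronger readings are tempting, but the documents do not support them:
- *The plan hides the harm.* It does not. Sections 11.0 and 13.0 provide for review every 25 patients and reporting to the IRB, so deaths would be recorded. What can be distorted is the efficacy comparison, and no comparison of deaths by arm is promised.
- *The plan treats a dead patient's mRS as missing.* It is silent. A known death might be given the scale's worst category.
- *The MAR rule makes an in-hospital death a short stay.* It does not, because that stay is observed. Section 15.0 does say that certain arms "may lead to a shorter hospital length of stay", so the handling should be stated, but the effect in step 5 is small.
- *Three deaths erase half to three quarters of the planned effect.* That uses one arm of 42 (57/42 = 1.36 to 87/42 = 2.07, or 49-74% of 2.8). Section 12.0 sizes the trial on pooled margins of 84.

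**Conclusion.** The gap is real and should be closed. Section 12.0 has one assumption for all missing scores, and no section makes an exception for death or for withdrawal because of deterioration. Applied as written, it biases PASS and AMPAC towards an arm with more such events. The mRS may be affected too, but there the conclusion rests on the plan's silence.

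On the primary outcome, three excess in-hospital deaths in a margin of 84 would shift the mean change by 0.7-1.0 points, about a quarter to just over a third of the planning difference. That rests on an assumed evaluation PASS of 15-25, an expected gain of 4 and a floor of 0. The effect of withdrawals has the same direction if those patients do worse than their earlier scores predict; its size cannot be derived from the documents. With no deaths and no such withdrawals, nothing changes.

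**What to change.** Add to Section 12.0:

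> Death is an outcome, not missing data. It takes the worst category of the mRS and counts as unfavorable in the binary analyses. PASS and AMPAC are also analysed with death at the lowest score or worst rank, as a pre-specified companion to the primary analysis, and deaths are reported by arm. Length of stay is reported with in-hospital deaths identified and not counted as early discharges. After withdrawal from study treatment, outcomes and vital status continue to be collected from the record and at the 30-day visit, unless the patient withdraws consent. MAR is the base assumption only for patients alive and unassessed for reasons unrelated to deterioration. A missing-not-at-random sensitivity analysis (delta or worst score) covers those withdrawn for worsening.

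Section 10.0 needs a matching field: vital status, with date of death, at discharge and 30 days. Section 14.0 needs a sentence separating the end of study treatment from the end of data collection. The reasons for stopping treatment need not change.

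Restricting MAR to everyone alive and unassessed would not be enough, because it would accept MAR for living patients withdrawn for worsening.

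Cost: a paragraph, one data field, a little more analysis work, and somewhat larger variance in the companion analysis if deaths occur.

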13.0 Risks, Discomforts and Potential Harms

Early mobilization in the acute stroke population may pose risks including but not limited to falls, decreased cerebral perfusion, worsening weakness and/or worsening stroke. The research team will monitor blood pressures before each PT session to make sure it is safe for the individual to participate. A confidentiality breach is also a risk associated with this research. However, no paper records will be stored or reviewed other than consent forms and only coded data will be used for the analysis. Identifying information will be removed from the primary database. Identifying information will be stored in a separate file with a unique identifier assigned to the patient to link the two datasets.

The PT treatment each participant receives may prove to be less effective or to have more side effects than the other study treatment(s) or other available treatments. The experimental treatments may have unknown side effects. The researchers will inform patients immediately if they learn anything during the course of the study that might make the patient change their mind about participating in the study.

Within the first 24 hours post admission for stroke, ALL patients will be returned to a semi-supine position with the head of bed angle <30-degrees to minimize the risk of decreased cerebral perfusion, which is standard of care. Despite the fact that the treatment group will be seen at an increased frequency for PT services- we will not increase their duration of upright within the first 24 hours of admission, which was thought in the previous AVERT trial to be the cause of poor outcomes. Thus, all patients will participate in PT services but will be placed back in a semi-supine position, less than 30-degrees following upright mobility.

The PI and Co-I's will meet every 25 patients to discuss data and safety monitoring. During these meetings we will look for any negative trends in the data we have collected (vitals, NIH stroke scale- i.e., stroke severity, and functional mobility scores) that could indicate adverse events and provide a timely summary report of adverse events to the IRB/NIH. If at any time, there is an adverse event (i.e.: worsened stroke or death) directly related to PT services at an increased frequency and intensity- the PI and/or Co-I's will alert the IRB immediately.

Precaution will be taken to lessen the probability of risks; despite increased frequency of treatments, duration of upright will still be approached cautiously within the first 24 hours s/p admission for stroke for cerebral perfusion. ALL stroke patients will be returned to semi-supine position within 24 hours of admission for acute stroke and maintain head of bed <30 degrees except for medication, meals, and therapy. They will only be upright for therapy services, medications, and meals- but will not be left in an upright seated position. Therapy will be

stopped if patient deemed medically unstable for increased frequency of treatments by the Stroke NP, Attendings, Fellow, or PI; this decision will be documented via “bed rest” orders in the patient’s electronic medical chart, so that the study team is aware to avoid progressive frequent upright mobilization.

Phase I of this study raised concerns regarding the risk of hypotension in patients’ status post external carotid stenting procedure and those patients were removed from the study secondary to medical instability and hypotension. Because of this, we will exclude patients who undergo external carotid stenting from participation in Phase II of this study. The American Association for Neurology also released clinical practice guidelines, attributing the negative effects of the AVERT trial to the hemorrhagic stroke population and warning against early mobility post hemorrhagic stroke. For this reason, we will only include ischemic strokes in Phase II of this study.

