6.0 Setting

This research will be conducted on the inpatient stroke service at MUSC (ED, 9E, 9W, 8W, ICU) as soon as possible after admission, ideally within the first 24 hours of the patient's admission to the vascular neurology service for an acute stroke. Follow up values will be collected at post discharge neurology clinic (either in person or through password protected zoom call, or doxy.me) by a member of the study team. Adverse events will be documented in the patient's medical chart and research record and the primary investigator will direct and oversee services provided.

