11.0 Data Management

Paper consent will be stored in a locked cabinet in the PT department. All data management will be conducted using the REDCap platform developed and housed at MUSC. All other collected data will be stored electronically in the MUSC OCIO approved secure SharePoint system.

Access to this database will be restricted based on netID permissions to a secured server and will only be accessible to IRB study personnel. Identifying information will be removed from the primary database. Identifying information will be stored in a separate file with a unique identifier assigned to the patient to link the two datasets.

Our data and safety monitoring plan will be continuous, close monitoring by the study investigator/co-investigators of all participants. The PI and Co-I's will meet every 25 patients to discuss data and safety monitoring. During these meetings we will look for any negative trends

in the data we have collected (vitals, NIH stroke scale- i.e., stroke severity, and functional mobility scores) that could indicate adverse events and provide a timely summary report of adverse events to the IRB/NIH.

Any reportable safety events that are unexpected, serious or may be related to the subjects' participation in this research will be reported to the MUSC IRB in accordance with their policies.

Once the Principal Investigator (PI) determines that an adverse event meets the IRBs' reporting requirements, the PI will report the SAE, and related safety information, to the IRB. For reasons of confidentiality, subjects' names will not be included in the report. If the adverse event results in the need to revise the informed consent, or other study documents, the PI will submit a study amendment to the IRB. Any trend in a type of adverse event will be relayed to the IRB as soon as the trend is noted. All events that do not meet the criteria of significant or trending, will be recorded in a summary form and included at the close of the study. Per consistency with the NIH guidelines- all serious and significant adverse events involving risks to a participant or suspension/termination of IRB approval for this study will be immediately reported to the sponsor.

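### Safety reviews every 25 patients: no section asks for worsened stroke, deaths and falls to be compared by randomised arm, at the reviews or at study end

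*Combined protocol and SAP*

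**What the plan says.** The review text appears in both section 11.0 (Data Management) and section 13.0 (Risks, Discomforts and Potential Harms). Every 25 patients the investigators will "look for any negative trends in the data we have collected (vitals, NIH stroke scale- i.e., stroke severity, and functional mobility scores", as possible signs of adverse events, and will "provide a timely summary report of adverse events to the IRB/NIH". Neither section mentions randomised arm.

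Other safety routes are in place:

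- Section 11.0 sends to the IRB "Any reportable safety events that are unexpected, serious or may be related" to participation, so attribution to physical therapy is not a precondition.
- Section 11.0 adds: "Any trend in a type of adverse event will be relayed to the IRB as soon as the trend is noted". Events that are neither significant nor part of a trend wait for a summary at study close.
- Serious and significant events go to the sponsor at once. The same sentence covers loss of IRB approval: "suspension/termination of IRB approval for this study will be immediately reported to the sponsor".
- Section 13.0 has an immediate IRB alert for an event such as worsened stroke or death that is "directly related to PT services at an increased frequency and intensity".
- Section 6.0 has adverse events recorded in the patient's "medical chart and research record and the primary investigator will direct and oversee services provided".

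On the hazards themselves, section 13.0 says that early mobilisation "may pose risks including but not limited to falls, decreased cerebral perfusion, worsening weakness and/or worsening stroke". Section 3.0 cites a previous trial that raised concern about worse stroke outcomes, mortality and falls. The endpoints in section 5.0 and the analysis in section 12.0 contain no between-arm comparison of these events. The nearest items are 30-day readmission (section 5.0) and complications (section 10.0).

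**The concern.** Worsened stroke, death and falls happen after acute stroke whatever therapy is given. A single event can rarely be attributed with confidence to an extra or harder session. In a randomised trial the evidence for harm is mainly a difference in event rates between arms, and the plan does not ask for that difference. A trend by type of event, which section 11.0 does relay, is a different quantity: it can rise or stay flat without showing where the events fall.

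At stake is whether the investigators and the IRB would have the comparison in front of them when judging if the more frequent or more intense arms should continue. The protocol itself raises this harm, so leaving the comparison unwritten is a weakness even though each event would still be recorded or reported.

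A smaller matter is section 14.0, which withdraws patients who become unstable or move to the ICU. It does not say that they stay in a safety count for their randomised arm. One sentence would settle this.

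**Working it through.** The documents give no figure for the safety reviews and no event rate by arm, so there is nothing to reproduce. The question is what a by-arm count could show, and when.

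**Inputs from the documents.** Reviews every 25 patients (sections 11.0 and 13.0). Allocation 1:1:1:1 (section 9.0). Total 168, so six reviews, at 25, 50, 75, 100, 125 and 150. Factorial margins as in the section 12.0 table, taking its High Duration row as the two frequent arms: frequency is C+D against A+B, intensity is B+D against A+C. Each margin holds about half the patients: 12, 25, 50 and 75 at the 25-, 50-, 100- and 150-patient reviews.

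**Assumptions.** One yes/no event per patient (worsened stroke, death or a fall). Rates of 15% vs 5% for a large excess, 10% vs 5% for a moderate one, and 10% or 5% in both margins for no excess.

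**Formula.** With X events among n patients in the frequent margin and Y among n in the other, both binomial and independent,

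P(X − Y ≥ 4) = Σ_i Σ_{j ≤ i−4} Bin(i; n, p₁) · Bin(j; n, p₂).

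The gap of 4 only measures how readable the table is.

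| Patients | n per margin | Expected events, 15% vs 5% | Gap ≥ 4: 15% vs 5% | 10% vs 5% | 10% vs 10% | 5% vs 5% |
|---|---|---|---|---|---|---|
| 25 | 12 | 1.8 vs 0.6 | 5.8% | 1.5% | 0.9% | 0.1% |
| 50 | 25 | 3.75 vs 1.25 | 30.7% | 11.0% | 4.8% | 1.2% |
| 100 | 50 | 7.5 vs 2.5 | 69.1% | 34.5% | 12.0% | 5.2% |
| 150 | 75 | 11.25 vs 3.75 | 86.7% | 52.7% | 16.9% | 9.2% |

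Each row is a single look at the frequency margin.

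**Repeated looks.** Simulating all six reviews and both margins with no true excess, a gap of 4 or more on the more frequent or more intense side arises at least once in about 40% of trials when the rate is 10% everywhere, and in about 22% when it is 5%.

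**Why arms as well as margins.** Suppose only the combined arm is harmful (15% vs 5%). At 150 patients there are 37.5 per arm, so 37.5 × 0.15 = 5.6 events in that arm and 37.5 × 0.05 = 1.9 in each other arm. The frequency margin then shows 5.6 + 1.9 = 7.5 against 1.9 + 1.9 = 3.8, which dilutes a threefold excess to a twofold one.

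**The case against.** The strongest reply is that silence about arms is not evidence of a pooled review. No section masks the investigators. They belong to the clinical team (section 7.0) and hold the research record (section 6.0). The immediate alert in section 13.0 refers to therapy at increased frequency and intensity, which presupposes knowing the allocation, and section 3.0 reports the Phase I event by arm. This stands. A reader might infer that reviewers would see only unsplit data, or that excess harm would pass unreported as isolated cases. The documents support neither. They support only that the comparison is not written down.

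The same sentence that names vitals, NIHSS and mobility scores also produces an adverse event summary, and section 13.0 gives worsened stroke and death as examples of adverse events. So deaths are not outside the review. Falls are the listed risk that the review text does not name.

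A reader might also infer that an unsplit total can never reveal harm. It can, if the background rate is known. At 150 patients with a 5% background, 12 or more events occur in 7% of trials without harm and in 83% with 15% vs 5%. The total fails when the background is uncertain: 10% everywhere and 15% vs 5% both give 15 expected events. The documents state no background rate, so splitting still helps.

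Nor does section 14.0 support a claim that events are lost at withdrawal. It removes nothing from safety reporting, and the event is known when the patient is withdrawn.

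Finally, the table is weak early and for moderate harm, and the exclusion of haemorrhagic stroke, stenting and unstable patients may keep rates low. That is correct and limits what the change can achieve.

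**Conclusion.** The concern holds in a limited form. Case-by-case and trend reporting are adequate as far as they go, but no section asks for harms to be compared by randomised arm, during the trial or at its end. A cheap improvement at meetings already planned is worth making.

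Its benefit is mainly for a large excess from mid-trial onward: under 15% vs 5%, about 31% at 50 patients and 69% at 100. It offers little at the first review (about 6%) and only about one chance in three at 100 patients for 10% vs 5%. These figures rest on assumed rates, a single composite event per patient and equal allocation. Real rates could be lower, and the table would then show less.

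**What to change.** Add to sections 11.0 and 13.0, and for the final analysis to section 12.0, text along these lines:

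> At each 25-patient meeting and at study end, the numbers of patients with worsened stroke, death, a fall, or any of these, regardless of attribution, will be tabulated by randomised arm and by frequency and intensity margin. Worsened stroke means a stated increase in NIHSS or a clinical diagnosis before discharge. Patients withdrawn under section 14.0 are counted in their randomised arm. The interim tables go into the summary to the IRB/NIH. PASS and AMPAC are not shown by arm at these meetings. The table informs judgement and is not a stopping rule.

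The sponsor needs to choose the NIHSS increase, because without it the counts would not be comparable between arms.

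The cost is a few sentences and one small table. Section 6.0 already requires adverse events to be documented, so little or no new data collection should be needed. There are two downsides. Investigators would see safety counts by arm, although the treating therapists necessarily know the allocation and the primary outcome stays unsplit at the reviews. Chance gaps will also prompt some discussion, at the frequencies given above, and this is the reason for not attaching a numerical trigger. Whether to pause stays with the investigators and the IRB.
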